7.9.1 Treatment Exposure and Compliance

Extent of exposure to study drugs will be summarized descriptively as the number of cycles started, duration of treatment, duration of treatment without full-day dose interruption (defined as full-day with 0 mg dose actually taken), cumulative total dose per subject, actual dose intensity and relative dose intensity.

The number and percentage of subjects with dose reductions, dose interruptions, dose interruptions ≥ 3 days that are not immediately followed by the end of treatment due to disease progression, and drug discontinuation will be tabulated, and the primary reason for dose modifications will be summarized.

The actual dose intensity (mg/day) is defined as the actual cumulative dose (mg) taken based on the total dose per day divided by treatment duration. The relative dose intensity (RDI) is defined as the ratio of actual dose intensity to the planned dose intensity (i.e. the initial assigned dose level in mg/day) in percentage.

Time to first occurrence of dose reduction/interruption due to an AE will be summarized descriptively. In addition, time to treatment failure, defined as time from start of study treatment to discontinuation of study treatment due to any reason, will be summarized.

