###### 3.1.1.1. Overall Description

*Patients:* The Phase 1 portion of the study will include patients with a histologically confirmed diagnosis of CLL/SLL or B-cell non-Hodgkin lymphoma.

*Design:* Eligible patients enrolled in sequential dose cohorts will receive once-daily, orally administered single-agent cerdulatinib at starting dose of 15 mg (15 mg po QD) in increasing dose levels until the MTD/MAD is identified. **An exception occurs on Days 2 and 3, during which patients on a QD schedule will not take study drug (see next paragraph).** If the MTD is not achieved, the highest studied dose will be declared the MAD and become the RP2D. (See [Table 3](#) for definitions of cancer types.)

To allow for a single-dose PK assessment, patients on a QD dosing regime will take their first dose of cerdulatinib on Day 1 and their second and subsequent doses daily beginning on Day 4. **They will not take cerdulatinib on Days 2 or 3.** Starting with Day 4, patients will receive cerdulatinib once daily for a total of 28 days (one cycle) to assess the MTD/MAD. Patients on BID dosing schedules can dosing begin on Day 1 and continue cerdulatinib without interruption (i.e., these patients will not skip any days of the cycle). If cerdulatinib is well tolerated, patients may continue to receive cerdulatinib at their assigned dose in the absence of disease progression, unacceptable toxicity, or meeting of any other withdrawal criteria (Section [4.4](#)).

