#### 5.1.2. Phase 1 Cerdulatinib Dosing

##### 5.1.2.1. *Initial Dosing with Cerdulatinib*

Following screening and confirmation of eligibility, patients will be sequentially assigned to the next open dose cohort. For QD dosing regimens, to allow for single-dose PK assessments during the Phase 1 portion of the study, patients will take their first dose of cerdulatinib on Day 1 and their second and subsequent doses daily beginning on Day 4. During Part 1 of the study, cerdulatinib will be taken orally once daily in the AM. For BID dosing regimens, BID dosing can begin on Day 1.

The initial dose cohort will begin treatment at a dose of 15 mg po QD. Subsequent total daily dose levels that may be studied include 30 mg, 60 mg, 90 mg, 120 mg, and 150 mg daily. Intermediate or higher dose levels may be studied, as appropriate, given the safety and PK profiles of cerdulatinib observed during the ongoing conduct of this study. Depending on the

PK profile, twice-daily administration (BID) may be considered during the course of dose escalation. Single-dose PK assessment will not be conducted for BID cohorts. Increments of dose escalation will be adjusted as needed to accommodate available capsule strengths. Every effort should be made to administer study drug at the same times each day.

Patients who do not receive at least 80% of their cerdulatinib doses in the first 28 days of treatment (Cycle 1) due to non-compliance will be withdrawn from the study. Beyond Cycle 1, dose holds may be permitted for reasons not related to disease progression or drug-related toxicity (e.g., elective procedures, vacations) with the permission of the Sponsor's Medical Monitor.

Intra-patient dose escalation will not be permitted during Phase 1.

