7.1.1. Definitions and Computations

Study treatment (study drug): cerdulatinib or rituximab

Study day: study day will be calculated relative to the date of the first dose of study treatment.

Treatment duration: date of last dose of study treatment – date of first dose of study treatment +1

Baseline: unless otherwise specified, a baseline value is defined as the last non-missing value collected on or before the first dose of study treatment (i.e. on/before Cycle 1 Day 1)

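### The SAP 7.9.1 dose-intensity formula treats the protocol's scheduled no-dose Days 2 and 3 as a shortfall, so fully compliant Phase 1 QD patients score below 100%

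*SAP*

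**What the plan says.** SAP 7.1.1 gives treatment duration as "date of last dose of study treatment – date of first dose of study treatment +1", a calendar span with no deduction for days on which no dose was due. SAP 7.9.1 divides the "actual cumulative dose (mg) taken based on the total dose per day divided by treatment duration" and takes the ratio of the result to the "planned dose intensity (i.e. the initial assigned dose level in mg/day". The list of exposure measures in SAP 7.9.1 also includes "duration of treatment without full-day dose interruption (defined as full-day with 0 mg dose actually taken". SAP 7.9 presents Phase 1 by starting dose level, so these rules apply to the escalation cohorts.

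For Phase 1 QD regimens, Protocol 5.1.2.1 says that "patients will take their first dose of cerdulatinib on Day 1 and their second and subsequent doses daily beginning on Day 4". Protocol 3.1.1.1 is explicit about the gap: "They will not take cerdulatinib on Days 2 or 3". The Synopsis and Section 3.1.1.1 both state that BID patients dose without a break. SAP 7.1.1, SAP 7.9.1 and the list of changes in SAP Section 8 contain no exception for the planned gap.

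**The concern.** RDI is normally read as the share of intended dose that a patient managed to take. Here the denominator expects the full assigned dose on every calendar day, while the protocol tells QD patients to take none on two of them. Perfect adherence therefore cannot give 100%, and the shortfall reflects the pharmacokinetic design and not tolerability.

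Phase 1 studied both QD and BID levels (Protocol 1.5 and the note to Table 7). The artefact touches only the QD levels, so a reader looking across dose levels in an exposure table would see a difference produced by the schedule. It is largest in patients who stop early, which is where exposure tables are most often read for signs of poor tolerability.

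**Working it through.** The documents state no dose-intensity figure, so there is none to reproduce. The check applies the SAP formulas to a patient who follows the protocol exactly.

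**Inputs**
- Duration N = last dose day - first dose day + 1 (SAP 7.1.1).
- Actual dose intensity = mg taken / N (SAP 7.9.1).
- Planned dose intensity = assigned dose d, in mg/day (SAP 7.9.1).
- QD schedule: a dose on Day 1, none on Days 2 and 3, then daily from Day 4 (Protocol 3.1.1.1 and 5.1.2.1).

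**Formula.** For N of at least 4, a compliant QD patient takes N-2 doses. Cumulative dose = (N-2)d, actual dose intensity = (N-2)d/N, and RDI = [(N-2)d/N]/d = (N-2)/N. The assigned dose cancels, so the shortfall is 2/N at every QD level.

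| Last dose on day N | Doses taken | RDI under the SAP | Shortfall (points) |
|---|---|---|---|
| 4 | 2 | 50.0% | 50.0 |
| 7 | 5 | 71.4% | 28.6 |
| 14 | 12 | 85.7% | 14.3 |
| 28 | 26 | 92.9% | 7.1 |
| 56 | 54 | 96.4% | 3.6 |
| 84 | 82 | 97.6% | 2.4 |
| 168 | 166 | 98.8% | 1.2 |
| 336 | 334 | 99.4% | 0.6 |

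Setting (N-2)/N to 95% gives N = 40, and to 99% gives N = 200, so a compliant QD patient reaches those values only from those days on. In mg terms, 45 mg QD over 28 days gives 26 x 45 / 28 = 1170/28 = 41.8 mg/day.

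**Cycle 1 wording.** The Synopsis implies 26 dosing days in 28. Section 3.1.1.1 can be read as Day 1 plus 28 daily doses from Day 4, which is 29 dosing days in 31. That gives 29/31 = 93.5%, and the conclusion does not change.

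**QD against BID.** A compliant BID patient has 28/28 = 100%. A BID patient with two unplanned full days off in 28 has 26/28 = 92.9%, the same value as a perfectly compliant QD patient.

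**Interruption-free duration.** Days 2 and 3 both meet the 0 mg definition, so a compliant QD patient treated for 28 days shows 26 uninterrupted days.

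**After correction.** With scheduled dosing days in the denominator, the compliant patient has (N-2)/(N-2) = 100% at every N of at least 4. Real non-adherence still shows: two further missed days in 28 give 24/26 = 92.3%, against 24/28 = 85.7% under the SAP.

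**The case against.** The strongest reply is that this is small. It affects only the QD patients among the 43 dosed in Phase 1, the shortfall is below 2.5 points from 84 days, and the documents do not say how many patients stopped early enough for it to be large. Exposure is descriptive, no QD-versus-BID test of RDI is planned, and the Phase 1 primary endpoint is the incidence of dose-limiting toxicity (DLT). All of that stands and sets the weight of the point. It could be added that the two-day offset is shared by all QD levels. That holds only at equal duration: because the shortfall is 2/N, a level with shorter treatment loses more. It is also possible that the Study Data Handling Document cited in SAP Section 8, which is not among the documents reviewed, contains an exception; the SAP text does not.

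A reader might infer more than the documents support:

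- *That every QD patient would be tabulated as interrupted.* The 0 mg definition is attached to interruption-free duration. The count of patients with interruptions is a separate statement, paired with reasons for dose modification, and the SAP does not say that the definition feeds it. A two-day gap cannot enter the category of "dose interruptions ≥ 3 days that are not immediately followed by the end of treatment due to disease progression".
- *That holds for toxicity before permanent discontinuation go unseen.* They fall outside RDI because duration ends at the last dose, which is a legitimate convention. SAP 7.9.1 still tabulates interruptions, discontinuations and their reasons, and its category of interruptions lasting three days or more leaves out only those that run into stopping for progression.
- *That Cohort 2 cerdulatinib duration runs to a rituximab date.* The definition "Study treatment (study drug): cerdulatinib or rituximab" allows that reading, but the text can equally be taken drug by drug. It concerns Phase 2a only and merits at most a clarification.
- *That DLT evaluability is affected.* The 80% rule in Protocol 5.2.1.1 refers to doses received in Cycle 1 and does not use RDI.

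**Conclusion.** The point holds, as a minor one. Taken literally, the SAP formula returns the wrong answer for a patient who did exactly what the protocol asked: RDI of (N-2)/N, which is 7.1 points short after one 28-day cycle and 2.4 points short at 84 days, plus two days lost from interruption-free duration. It is limited to Phase 1 QD patients whose last dose is on Day 4 or later; BID cohorts and Phase 2a are unaffected. Only descriptive exposure summaries change, and no DLT or efficacy conclusion depends on them.

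This rests on two assumptions: that the formulas are programmed as written, and that no exception exists in the data handling document.

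**What to change.** In SAP 7.9.1, for Phase 1 QD cohorts:

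- Define planned cumulative dose as the assigned dose times the number of protocol-scheduled dosing days between first and last dose. That number is duration - 2 when duration is 4 days or more, and 1 when only the Day 1 dose is taken. The condition is needed because an unconditional duration - 2 gives a negative planned dose for a patient with a single dose.
- Compute RDI as actual over planned cumulative dose. For all other cohorts, planned cumulative dose is assigned mg/day times duration, which reproduces the present formula.
- State that the scheduled no-dose Days 2 and 3 are not full-day interruptions.

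Optionally, add one sentence that cerdulatinib exposure uses cerdulatinib dates only.

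The cost is a few lines of SAP text and derivation code. Dosing and data collection do not change.

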**3.1.3. End of Study**

The end of study will occur when all patients have completed the follow-up visit at 30 days post-treatment, or until all patients have died, have been discontinued (under advice of the physician, at the request of the Sponsor), have withdrawn consent, or are lost to follow-up, whichever occurs first.

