**3.1.4. Total Number of Patients, Cessation of Treatment, and Total Duration of the Study**

Under Phase 1 (closed to enrollment), 52 patients were enrolled, and 43 were dosed. Under Phase 2a, approximately 240 patients can be enrolled. Thus, a total of up to 283 patients can be dosed in the study.

Patients enrolled under Phase 1 and Phase 2a may continue to receive cerdulatinib or cerdulatinib in combination with rituximab (in the combination cohort No. 2; see [Table 6](#)) in the absence of disease progression or intolerable toxicity, until they meet any other withdrawal criteria, (Section 4.4) or until the end of study (defined in Section 3.1.3).

The total duration of the study is expected to be approximately 6 years.

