##### 4.4.1. **General Withdrawal Criteria**

Discontinuation of study drug and/or withdrawal from the study will occur if any of the following apply:

- The patient experiences disease progression requiring other therapy.
- The patient develops intolerable toxicity.
- The patient develops an intercurrent condition precluding further administration of cerdulatinib.
- The patient withdraws consent for further participation in the trial.
- The patient becomes pregnant.
- The patient fails to comply with study drug administration, dosing evaluations, or other requirements of the study.
- The patient needs a concomitant medication that makes the patient ineligible for further participation in the study.
- The Investigator believes it is no longer in the best interest of the patient to receive cerdulatinib.
- The Sponsor discontinues the trial.

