**4.6. Sponsor Study Discontinuation**

The Sponsor has the right to terminate the entire study or study cohorts at any time. Reasons for terminating the study or study cohorts may include, but are not limited to, the following:

- Excessive toxicity indicating a potential health hazard to patients.
- Poor patient enrollment.

The Sponsor will notify the Investigator if the study is placed on hold (or if individual cohorts are placed on hold), or if the Sponsor decides to discontinue the study or program.

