5.2. Phase 2a Sample Size

Each of the 6 cohorts will consist of approximately 20 to 50 patients with relapsed or refractory disease. Initial enrollment into any cohort will be up to 20 patients; cohorts may be expanded to 40 to 50 evaluable patients. A total of approximately 240 patients are planned. If fewer than 2 responses are seen in the first 20 patients, enrollment in the cohort will be closed, as the upper bound of the 95% confidence interval would be approximately 25%. If 2 or more responses are seen, the cohort may be expanded.

Patients in Cohorts 1, 3, 4, 5, and 6 will receive single-agent cerdulatinib. Patients in the Cohort 2 will receive cerdulatinib in combination with rituximab. The composition of each cohort is described in Table 6 of section 3.1.2 of the protocol.

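### Time to treatment failure counts administrative termination by the sponsor as failure, so this descriptive summary depends on closure dates

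*SAP*

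**What the plan says.** SAP 7.9.1 (Treatment Exposure and Compliance) plans a summary of "time to treatment failure, defined as time from start of study treatment to discontinuation of study treatment due to any reason". It attaches no exception and no censoring rule.

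Protocol 4.4.1 opens its list with "Discontinuation of study drug and/or withdrawal from the study will occur if any of the following apply", and the last entry is "The Sponsor discontinues the trial". Protocol 4.6 adds "The Sponsor has the right to terminate the entire study or study cohorts at any time", with excessive toxicity and poor enrollment as examples of why. Treatment has no fixed length. Under Protocol 3.1.4, "Patients enrolled under Phase 1 and Phase 2a may continue to receive cerdulatinib or cerdulatinib in combination with rituximab" while there is no progression, intolerable toxicity or other withdrawal criterion, "or until the end of study (defined in Section 3.1.3").

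Three other parts of the SAP bear on the point:

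- Section 7.1 makes Kaplan-Meier the default for time-to-event variables.
- Table 1 in Section 7.8.2.1 gives censoring rules for PFS, and Section 7.8.2.2 extends them to DOR. They are not extended to time to treatment failure.
- Section 7.2 tabulates the primary reason for treatment discontinuation.

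**The concern.** A stop ordered because the sponsor closes the study or a cohort for, say, slow accrual says nothing about whether treatment was working. Read literally, the definition still makes it a failure on the closure date. The patients affected are those still on drug at that moment, who tend to be the ones doing well and the ones enrolled late. The summary is then pulled downward by an amount set by accrual and closure dates.

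The stakes are limited but not nil. SAP 7.8 and Section 8 confine aggregated efficacy to FL in Cohorts 1 and 2 and PTCL in Cohort 5; other patients get listings only. Exposure, by contrast, is summarized by cancer type in the whole safety population. For the aggressive NHL, CLL/SLL and CTCL patients, time to treatment failure is therefore one of the few aggregated figures that a reader could take as a sign of durability. The protocol synopsis says that Cohorts 1, 3 and 4 opened first and that others may open or close at the sponsor's discretion, so potential follow-up can differ between cancer types.

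**Working it through.** **Reading the rules together.** Take a patient in response whose drug stops only because the sponsor ends the cohort.

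1. SAP 7.9.1: treatment was discontinued, the reason is immaterial, so this is an event on that date.
2. SAP 7.1: Kaplan-Meier censors patients who have not had the event. It cannot censor a stop that the definition calls an event.
3. SAP Table 1: for PFS the same patient, alive without documented progression, is censored at the last disease assessment.

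The same patient at the same closure is thus censored for PFS and a failure here.

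**Overlap with duration of treatment.** SAP 7.1.1 defines treatment duration as last dose date minus first dose date plus 1, and 7.9.1 already reports it. For a patient who has stopped, time to any-reason discontinuation largely repeats that quantity under the label 'failure'.

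**Size.** The plan states no figure for this item, so there is nothing to reproduce. All inputs below are assumptions:

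- T, time to a stop other than closure, is exponential with median m months: S(t) = 2^(−t/m).
- U, time from first dose to closure, is uniform on (F, F+A) months and independent of T: G(t) = 1 for t ≤ F, and (F+A−t)/A from F to F+A.
- Every patient still on drug at closure is stopped by the sponsor.

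If closure is censored, the curve estimates S(t). If closure is an event, it estimates S(t) × G(t), and its median solves S(t) × G(t) = 0.5. The share still on drug at closure is [m/(A ln 2)] × [2^(−F/m) − 2^(−(F+A)/m)].

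With m = 10, F = 6, A = 36:

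- Share on drug at closure: 14.427/36 × (0.660 − 0.054) = 0.24.
- 12 months: S = 2^(−1.2) = 0.435; G = 30/36 = 0.833; product 0.363.
- 18 months: S = 2^(−1.8) = 0.287; G = 24/36 = 0.667; product 0.191.
- Median: at t = 8.8, 2^(−0.88) × 33.2/36 = 0.543 × 0.922 = 0.501, so about 8.8 months instead of 10.0.

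Varying both the true median and the follow-up window:

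| True median (months) | Follow-up window (months) | On drug at closure | Median, closure counted | 12-month rate: censored / counted |
|---|---|---|---|---|
| 4 | 6–42 | 6% | 4.0 | 12.5% / 10.4% |
| 8 | 12–48 | 11% | 8.0 | 35.4% / 35.4% |
| 8 | 3–27 | 32% | 6.3 | 35.4% / 22.1% |
| 10 | 6–42 | 24% | 8.8 | 43.5% / 36.3% |
| 12 | 12–48 | 21% | 12.0 | 50.0% / 50.0% |
| 12 | 6–42 | 30% | 10.0 | 50.0% / 41.7% |
| 12 | 3–27 | 46% | 8.0 | 50.0% / 31.2% |
| 18 | 0–24 | 65% | 7.8 | 63.0% / 31.5% |

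The median is unchanged when every patient's follow-up is at least as long as the true median. The effect is largest with long treatment and short follow-up.

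**The case against.** The strongest reply is that this is an exposure summary and is defined openly. Time to discontinuation for any reason is a legitimate, reproducible measure of time on drug. It sits beside cycles started and dose intensity, no test or decision uses it, and the reasons for stopping are tabulated in the same report. Most of this stands, and it is why the point is minor. It does not remove the problem: the table of reasons lets a reader count sponsor-driven stops but does not correct the curve or the median, and a plain time-on-drug measure needs neither the word 'failure' nor a second copy of treatment duration.

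A reader might also infer more than the documents support:

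- *That efficacy results are biased.* ORR, PFS and DOR have their own definitions in SAP 7.8 and do not use this variable.
- *That cohort futility closure creates failures.* The rule reads "If fewer than 2 responses are seen in the first 20 patients, enrollment in the cohort will be closed". It stops accrual, not treatment; only termination under Protocol 4.6 matters here.
- *That end of study is a fixed date that cuts treatment off.* Protocol 3.1.3 defines it mainly by patients having finished their post-treatment visit, died, withdrawn or been lost. Its reference to patients who "have been discontinued (under advice of the physician, at the request of the Sponsor") only repeats the power in 4.4.1 and 4.6.
- *That patients on drug at data cutoff are failures.* They have not discontinued, and the Kaplan-Meier default implies censoring, though the SAP does not say so for this item.
- *That a planned comparison between cohorts is invalidated.* None is planned on this variable.

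The documents do not show that an administrative termination has happened or is intended. The calculation also leans high within each window, because it lets no one be censored at a cutoff before closure.

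**Conclusion.** The point holds as a minor one. By its stated rule, SAP 7.9.1 scores as a treatment failure any patient whose drug stops only because the sponsor administratively ends the study or cohort, and nothing else in the SAP censors that stop. The summary would then be biased downward and depend on closure dates.

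The documents cannot fix the size. In the illustrative case (true median 10 months, window 6 to 42 months), the 12-month rate drops by about 7 percentage points and the median by about 1.2 months. Across the scenarios shown, the loss in the median runs from none to about 10 months (18 to 7.8, with follow-up starting at zero). All of this assumes exponential time on drug, uniform follow-up independent of it, and sponsor termination of everyone still on drug. If no administrative termination takes place, there is no effect.

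**What to change.** In SAP 7.9.1, keep discontinuation for any reason as the event and add one exception: in the Kaplan-Meier estimate, censor at the last dose date patients whose drug stops only because the sponsor administratively ends the study or cohort. State in the same place that patients still on drug at data cutoff are censored. Keeping the any-reason event avoids having to place each remaining Protocol 4.4.1 reason, such as pregnancy or non-compliance, on a new event list.

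Because Protocol 4.6 also names excessive toxicity, do not censor terminations made on that ground: keep them as events or report them separately.

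First confirm that the recorded discontinuation reason distinguishes sponsor termination. SAP 7.2 plans to tabulate the reason but does not list the categories. If it does, the cost is a sentence or two in the SAP and one censoring flag, with no new data. The downside is that the measure is no longer strictly all-cause. If the all-cause measure is preferred, rename it time to treatment discontinuation and show the number of sponsor-driven stops beside it.
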